Subject visits will be conducted in the CRC at BIDMC or, rarely, in private patient exam rooms in the dermatology clinic if the CRC is not available at the time of subject visits. Both locations should ensure adequate privacy for patients. Patients will complete all study related procedures in these private settings, including questionnaires. Questionnaires will be in written form and returned directly to the investigators or study staff.

Pre-screening telephone calls and subject visits will be limited only to the minimum amount of data necessary to accomplish the research purposes. No sensitive questions will be discussed by telephone.

Physical Setting

Subject visits will be conducted in the CRC at BIDMC or, rarely, in private patient exam rooms in the dermatology clinic if the CRC is not available at the time of subject visits. Both locations should ensure adequate privacy for patients. Patients will complete all study related procedures in these private settings, including questionnaires.

B8. DATA SECURITY

All subjects will be assigned a subject number at their screening visit. Only investigators and study staff at BIDMC will have access to the subject's identifiable health information. To ensure appropriate privacy and confidentiality, any paper source documentation and questionnaires will be stored in a locked cabinet. Only the PI, sub-investigator, and study staff will have access to this locked cabinet. This documentation will all be coded. Subject's identifiable health information will be kept separate from coded documentation. Any electronic data containing PHI will be stored on a password protected computer in a locked office and on a secure server behind the BIDMC firewall.

The Investigator will maintain adequate records for the study, including source documentation, Informed Consent documents, drug dispensing and disposition records, information regarding participants who discontinued, adverse events, and other pertinent data. All essential documents will be retained by the Investigators for at least 10 years in a long-term storage facility as arranged through the CTO.

B9 Multi-Site Studies

Is the BIDMC the coordinating site? Yes No

Is the BIDMC PI the lead investigator of the multi-site study? Yes No

B10 Dissemination of Research Results

Subjects will be thanked for their participation in the study immediately following their last visit. Because we are not able to anticipate the final completion date of the study, which may take years, and because we are not primarily responsible for analyzing and publishing the data, it will not be feasible for investigators to provide results to individual subjects. Subjects may contact the PI following their completion of the study to inquire about the final findings of the study, if available to the investigators, at that time.

Planned dissemination of research results may include abstract presentations at dermatology conferences and submission of data for publication in academic journals as an original research article.

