Kato et al subsequently reported a 66 year old woman with typical clinical and histopathological features of NLD without diabetes mellitus. [2] In their report, immunohistochemical staining found IL-17 expression present in lymphocytes, macrophages, multinucleated giant cells, and a high density of IL-17 expressing T-cells in granulomatous regions and around blood vessels. Together these cases suggest that NLD may be an inflammatory disorder involving TH17 cells and that vessels may be the target of inflammation. This may, in part explain, previous reports of patients with NLD who have been successfully treated with TNF-alpha antagonists. Finally, Wakatsuki has reported a patient with concurrent NLD and palmoplantar pustulosis (PPP). Immunohistochemistry performed on biopsy specimens found IL-17 producing cells densely associated with NLD lesions, as well as PPP lesions.

Rationale:

The reports described above suggest a possible role for IL-17 in the pathogenesis of NLD, and raise the possibility that blockade of IL-17 may be a potential therapeutic strategy in patients with NLD. Secukinumab is a human monoclonal antibody that targets IL-17a, approved by the FDA for the treatment of psoriasis. Several phase III studies have found this medication to be largely safe with nasopharyngitis and headache reported as the most frequently observed adverse events.

An open-label proof of concept study regarding the use of secukinumab in patients with NLD may be a first step in elucidating and defining a definitive treatment for this chronic and potentially debilitating condition for which no FDA approved treatment currently exists.

B3. DESCRIPTION OF RESEARCH PROTOCOL

A. Study Design – Overview, Methods, Procedures

Study Design

This study is a non-randomized, open-label, proof of concept study. Eighteen patients aged 18 and over with histopathologically-proven NLD will be included in a prospective non-controlled study. Dosage of Secukinumab will be given according to the standard therapy regimen for psoriasis (300 mg q weekly for 5 weeks followed by 300 mg q 4 weeks). The study comprises a 2-week screening period, a 24-week open-label study period, and a 12-week follow-up period. The follow-up period consists of a phone call 16 weeks after the last study drug dose.

Population

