Patients potentially eligible for this study are at least 18 years of age and have histologically confirmed necrobiosis lipoidica diabetorum. A total of 18 subjects will be enrolled in the study. Potential patients will be assessed for eligibility to participate in this clinical study using the criteria for inclusion and exclusion listed under “Subject Selection” section.

Methods

Study Endpoints:

1. Primary Endpoint

- **Proportion of patients achieving remission or clinical improvement based on Investigator Global Assessment Score as measured at week 24.**

2. Secondary Endpoints

- **Proportion of subjects achieving improvement based upon histological score**
- **Proportion of subjects improving based upon patient-reported outcomes (pain score and Dermatology Quality of Life Index Score)**

Investigator Global Assessment (IGA) of Efficacy Score (See Investigator Global Assessment of Efficacy Score)

(adapted from scoring system for published pyoderma gangrenosum trials)

Score	Description
0	Completely clear: except for possible residual hyperpigmentation
1	Almost clear: very significant clearance (about 90%); however, patchy remnants of dusky erythema and/or very small ulcerations
2	Marked improvement: significant improvement (about 75%); however, a small amount of disease remaining (i.e. remaining ulcers, although have decreased in size, minimal erythema and/or active boarder)
3	Moderate improvement: intermediate between slight and marked; representing about 50% improvement
4	Slight improvement: some improvement (about 25%); however, significant disease remaining (i.e. remaining ulcers with only minor decrease in size, erythema or boarder activity)
5	No change from baseline
6	Worse

Scoring system based on the following trial [4]:

An open-label pilot study of alefacept for the treatment of pyoderma gangrenosum. European Academy of Dermatology and Venereology 2008 22, pp943–949

Histological Score

- a. Inflammatory infiltrate (0, none; 1, slight; 2, moderate; 3, severe)
- b. collagen degeneration (0, none; 1, slight; 2, moderate; 3, severe)
- c. epithelioid histiocytes, (0, none; 1, slight; 2, moderate; 3, severe)
- d. qualitative expression of IL-17 (0, none; 1, slight; 2 moderate; 3, severe)

Scoring system based on the following trial [5]:

Fumaric acid esters in necrobiosis lipoidica: results of a prospective noncontrolled study. British

Journal of Dermatology 2005 153, pp802–807

Patient-Reported Outcomes

Pain Score

- _(i) Resolved

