Skin biopsies will be sent to Dermatopathology lab at BIDMC for further Immunohistochemistry analysis as below. Samples will be preserved in formalin jars and sent to the histology lab to be processed within 48 hours. The paraffin blocks will be sectioned and stained at the histology lab, and then blocks and slides will be returned to the Dermatopathologist and stored securely at BIDMC, Dept of Pathology. Samples are retained for the duration of the project, through publication. If all

members of the study team deem they are no longer needed, they will then be destroyed.

Immunohistochemistry

Each biopsy will be fixed in formalin, bisected vertically, dehydrated by routine histologic methods, and embedded in a paraffin block. 5- μ m-thick surface sections will be cut, mounted on glass slides, and baked for 60 minutes at 60C. The first slide will be stained with Hematoxylin and Eosin. The next slide will be loaded into the Bond III staining platform and antigen retrieved by immersion in Bond Epitope Retrieval 2 for 30 minutes. It will then incubated at room temperature for 30 minutes with Anti-Human IL17A antibody [Abcam 4K5F6] at a concentration of 0.5–10 μ g/ml. After appropriate washes, antibody detection will be performed using Bond Polymer Refine Detection kit. Slides will be developed in DAB, then dehydrated and coverslipped. A biopsy of an active psoriatic skin lesion and a slide of the case with no antibody applied will be run in parallel as positive and negative controls, respectively.

Evaluation of immunohistochemistry

IL-17A expression levels will be scored as follows: A three tier stratification threshold for percentage of positive lymphocytes will be established after review of the pre-treatment biopsies, and classified as absent, low, or high. Cellular staining intensity will be scored as 0 (no staining), 1 (weak staining), 2 (moderate staining), or 3 (strong staining).

Pre- and post-treatment expression levels will be compared using Fisher's exact test. Pre-treatment IL17A expression level will be compared with clinical response parameters and evaluated as a possible predictor of response to therapy.

In case of an adverse event or disease progression, patients are instructed to call and/or visit the clinic trials unit at Beth Israel Deaconess Medical Center. Any visits will be recorded on source documentation as Unscheduled Visits. Any of the procedures may be performed at an unscheduled visit at the discretion of the investigator.

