Any medication or surgical treatment that will be used to treat AEs will be recorded on the electronic case report forms (eCRF).

Prohibited Therapy

The treatments listed below are prohibited for all subjects during the study:

- Any investigational agent
- Any immunosuppressive systemic therapy started within 28 days prior to baseline, including but not limited to oral corticosteroids, adalimumab or other biologic agent, etc.
- Surgical intervention on the treatment areas

Investigational Product/Study Drug

Secukinumab (Cosentyx)

Secukinumab (Cosentyx) is a human monoclonal antibody that targets IL-17a and is FDA approved for the treatment of psoriasis, psoriatic arthritis, and ankylosing spondylitis.

COSENTYX injection is a sterile, preservative-free, clear to slightly opalescent, colorless to slightly yellow solution. COSENTYX is supplied in a single-use Sensoready pen with a 27-gauge fixed ½-inch needle, or a single-use prefilled syringe with a 27-gauge fixed ½-inch needle. The removable cap of the COSENTYX Sensoready pen or prefilled syringe contains natural rubber latex.

Each COSENTYX Sensoready pen or prefilled syringe contains 150 mg of secukinumab formulated in: L-histidine/histidine hydrochloride monohydrate (3.103 mg), L-methionine (0.746 mg), polysorbate 80 (0.2 mg), trehalose dihydrate (75.67 mg), and Sterile Water for Injection, USP, at pH of 5.8.

Secukinumab will be supplied by the sponsor, Novartis, and will be packaged in quantities sufficient to accommodate study design. Each kit will be labeled per local requirements and this label must remain affixed to the kit. Upon receipt, study drug should be stored as specified on the label in their original packaging and kept in a secure location. A temperature log will be maintained for documentation in the research pharmacy. Administration of the study drug will be recorded by study

personnel at scheduled study visits.

Summary of findings from clinical and non-clinical studies

Secukinumab is a recombinant human monoclonal IgG1/κ antibody that binds specifically to IL-17A. It is expressed in a recombinant Chinese Hamster Ovary (CHO) cell line. Secukinumab has a molecular mass of approximately 151 kDa; both heavy chains of secukinumab contain oligosaccharide chains. Please refer to the local label available to you for information regarding the efficacy and safety of this product.

Overview of Study Procedures:
Evaluation Schedule:

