The clinical efficacy will be measured by physician assessments and standardized scoring tools as noted in Main Study Parameters and Secondary Parameters. Because of the small number of patients in the study, and absence of a control group, primarily descriptive statistics will be used to report data from measured endpoints.

Main Study parameters

Primary Endpoint

- Proportion of patients achieving remission or clinical improvement based on Investigator Global Assessment Score as measured at week 24.

We will assess the proportion of patients achieving remission or clinical improvement based upon the previously published Investigator Global Assessment Score. Remission correlates with a score of 0 or 1 and clinical improvement correlates with at least a -1 change from baseline.

Secondary study parameters

Secondary Endpoints

Because of the small sample size, primarily descriptive statistics will be used.

- Proportion of subjects achieving improvement based upon histological score
- Proportion of subjects achieving improvement based upon patient-reported outcomes (pain score and Dermatology Quality of Life Index Score)

Other study parameter(s)

Patient characteristics and demographic data will be presented using descriptive statistics.

Histological Score

In addition, a histological score will be calculated as a secondary endpoint. The score is calculated by adding sub scores as listed below, which will be evaluated by the dermatopathologist. Average of pre and post scores and overall change in score will be calculated and compared using a paired T-test. See Secondary Study Parameters for details regarding histologic analysis.

Pain Score

A Pain Score will be calculated based upon the Wong-Baker 10-point pain score, which has been widely used to rate pain in both children and adults and has also been used in dermatology clinical trials.[6]

Response based on an improvement from baseline in the Wong-Baker pain score at all scheduled time points will be calculated. We will compare pre and post treatment pain values and categorize patients as

Dermatology Life Quality Index (DLQI)

A Quality of Life Score will be calculated based upon the Dermatology Life Quality Index (DLQI).

C. Subject Selection

Inclusion Criteria

A subject must meet all of the following criteria in order to be eligible to participate in this study:

1. Adults, age 18 and over
2. Previous diagnosis of biopsy-proven NLD
3. Active NLD lesions, defined as

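### The secondary histological score appears to add IL-17 expression, the drug's own target, to three tissue items, with no separate tissue result and no masked slide reading planned

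*Combined protocol and SAP*

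**What the plan says.** **Endpoint.** One secondary endpoint is "Proportion of subjects achieving improvement based upon histological score" (B3.A, Secondary Endpoints; repeated in B3.B). No threshold for improvement is given.

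**Items.** B3.A, Histological Score, lists (a) inflammatory infiltrate, (b) collagen degeneration, (c) epithelioid histiocytes and (d) "qualitative expression of IL-17 (0, none; 1, slight; 2 moderate; 3, severe". Each runs from 0 to 3.

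**Scoring and analysis.** B3.B, Histological Score: "The score is calculated by adding sub scores as listed below, which will be evaluated by the dermatopathologist". No list follows there, so the B3.A list is the only candidate. Then: "Average of pre and post scores and overall change in score will be calculated and compared using a paired T-test". The preceding section on secondary parameters adds the limit "Because of the small sample size, primarily descriptive statistics will be used".

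**IL-17 elsewhere.** The drug is described as an "antibody that binds specifically to IL-17A" (B3.A, Summary of findings). Evaluation of immunohistochemistry plans its own IL-17A analysis: "Pre- and post-treatment expression levels will be compared using" Fisher's exact test. It uses three tiers for the percentage of positive lymphocytes and a 0 to 3 staining intensity. Neither scale is mapped to item d.

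**Masking.** B3.A, Randomization, blinding and treatment allocation, states that the study has neither randomization nor blinding. No section makes an exception for the dermatopathologist's reading.

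**The concern.** The study's purpose is to see whether the drug shows evidence of efficacy. Without a control arm, histology could give an efficacy reading less open to expectation than the investigator's global assessment. Two features weaken it.

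First, a sum of a to d mixes two questions: did the tissue improve, and did staining for the drug's target fall? A one-point fall in d alone lowers the total, feeds the t-test and, under an any-drop definition, makes the subject improved. The separate IL-17A analysis does not resolve this. Its scales are not tied to item d, so a reader cannot subtract it from the total to recover a to c.

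Second, a reader who knows which slide is post-treatment may score it lower on any item, and a before-and-after comparison has nothing to offset that.

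**Working it through.** The plan gives no maximum score, power, significance level or sample-size calculation, so there is no figure to reproduce.

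**1. Range (inferred from the B3.A list).** Total: 4 × 3 = 12. Items a to c: 3 × 3 = 9. Share of item d: 3/12 = 25%.

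**2. What is promised.**

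| Quantity | Planned result |
|---|---|
| Total (a to d) | Pre and post averages, change, paired t-test, proportion improved |
| IL-17A | Fisher's exact test, on other scales |
| a + b + c | None |

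**3. Illustration for the t-test.** From the documents: n = 18. Assumed: two-sided 5% level; each of the four items independently changes by −1, 0 or +1 with probabilities e/2, 1 − e and e/2, for e = 0.1, 0.2 or 0.3; floor and ceiling ignored; no true change in a to c; item d additionally falls by 1 in k subjects. Simulated chance of a significant fall in the total (200,000 trials per cell):

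| k of 18 | e = 0.1 | e = 0.2 | e = 0.3 |
|---|---|---|---|
| 0 | 2% | 2% | 2% |
| 4 | 18% | 13% | 10% |
| 9 | 74% | 50% | 37% |

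On a + b + c alone it stays near 2% whatever happens to d.

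**4. Four subjects.** The paragraph on the follow-up call after study completion mentions 3 completers and 1 early termination. With d falling in 2 of 4, the same model gives a significant fall in at most about 3% of trials. Without noise, p = 0.182 for 2 of 4 and p = 0.058 for 3 of 4. The t-test concern is then negligible.

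**5. Proportion improved, any-drop definition (assumed).** For a + b + c with no true change, P(drop) = [1 − P(sum = 0)]/2, where P(sum = 0) = (1 − e)³ + 6(e/2)²(1 − e).

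- e = 0.1: P(sum = 0) = 0.729 + 0.0135 = 0.7425, so P(drop) = 0.129.
- e = 0.2: 0.512 + 0.048 = 0.560, so 0.220.
- e = 0.3: 0.343 + 0.0945 = 0.4375, so 0.281.

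For the total, let S be the sum of the four noise terms. If d falls by 1, P(drop) = P(S ≤ 0); otherwise it is P(S < 0). When d falls in half the subjects (9 of 18 or 2 of 4), the expected proportion is [P(S ≤ 0) + P(S < 0)]/2. By symmetry P(S < 0) = P(S > 0) = 1 − P(S ≤ 0), so this is exactly 50% for every e. The comparison is 50% on the total against 13%, 22% or 28% on a + b + c.

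**The case against.** **IL-17 belongs in the score.** The background says one case report "found IL-17 expression present in lymphocytes, macrophages, multinucleated giant cells" in NLD tissue. A fall in d may therefore be real response, and scoring it in a proof-of-concept study is defensible. This stands. It is a reason to keep the total, not to leave its parts unreported.

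**The drug must lower the staining, so the score is built to succeed.** A reader might infer this, but the documents contain no data on the drug's effect on IL-17 staining. The number of subjects in whom d falls is assumed throughout.

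**Four of 18 is enough for significance.** A reader might also infer this. With d down one point in 4 of 18 and nothing else moving, the mean change is −4/18 = −0.222, t = −2.20 and p = 0.042. That requires no reading noise in any item; with noise in all four, the same case is significant in only 10% to 18% of trials. The 5% level is itself an assumption. Treating d as independent of a and c is also unfavourable to the plan, because the background places IL-17 in the same inflammatory cells.

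**Summing d is an inference.** True: the list announced in B3.B is absent, and the B3.A list is only the best candidate.

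**No blinding is declared.** The statement stands under an allocation heading, so it may not have been written with slide reading in mind. Either way, open-label treatment does not prevent masked reading.

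**Items a to c can be tabulated later.** They can, since sub scores are evaluated for each biopsy. Unplanned, however, the choice of which score to stress stays open until results are seen.

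**Conclusion.** The point holds as a modest one about interpretability and reader bias. On the most natural reading of the two sections, a fall in the total or in the count of improved subjects cannot show whether tissue changed or only IL-17 staining did, and unmasked reading can bias either.

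The structural point does not depend on the simulations. Its size is unknown, and the percentages show only what is possible under the stated assumptions. If the data come from about four subjects, what remains is a shifted proportion improved, made worse by the lack of a definition of improvement.

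The primary endpoint is untouched. The documents do not support saying that the score is invalid, that the drug's effect on d is assured, or that the total must be replaced.

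**What to change.** 1. **Report the parts.** Keep the planned four-item total. Beside it give a + b + c (0 to 9) and item d separately: pre, post, change, and proportion improved under one stated definition fixed before the masked reading. Label a + b + c as added after some subjects had finished. Do not describe a fall in the total as tissue improvement unless a + b + c also falls. State in B3.B which items are summed. No cut-off is proposed here: under the noise model with no true change, requiring a drop of at least 2 on a + b + c cuts false improvement from 13%, 22% or 28% to 0.7%, 2.5% or 5.1%, but detection of a true one-point fall goes from 87%, 78% or 72% to 13%, 22% or 28%.

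2. **Mask the reading.** Have the same dermatopathologist read coded slides in random order, masked to subject and time point. Blocks and slides are retained, so this is feasible.

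3. **Separately, reconcile the biopsy timing.** Skin Biopsy puts the second biopsy at week 26, but the evaluation schedule marks it at week 24 and shows only suture removal at week 26. The Early Termination Visit copies week 26, so it is unclear whether subjects who stop early have a paired score.

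**Cost.** Wording and slide coding; no extra biopsy, visit or reader. Slides already scored need re-reading: up to 4 × 2 = 8 biopsies if the four subjects mentioned each had both. With so few slides the reader may recall some, and the baseline slides reviewed to set the IL-17A tiers will already be known, so masking would be imperfect.

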- (ii) Improved
- (iii) Stable
- (iv) Worsened

Dermatology Life Quality Index (DLQI)

A Quality of Life Score will be calculated based upon the Dermatology Life Quality Index (DLQI). The DLQI is a validated general dermatology questionnaire that consists of 10 items that assess subject health-related quality of life (daily activities, personal relationships, symptoms and feelings, leisure, work and school, and treatment) (See Dermatology Life Quality Index). [7] It has been extensively used in dermatology clinical trials for AD. The DLQI is a psychometrically valid and reliable instrument that has been translated into several languages, and the DLQI total scores have been shown to be responsive to change. The minimally important difference for the DLQI has been estimated as a 2 to 5 point change from baseline.

Other study parameters

Safety Parameters

Safety evaluations include adverse event (AE) monitoring, physical examinations, vital sign measurements, and clinical laboratory testing (hematology and chemistry) as a measure of safety and tolerability for the entire study duration.

At every visit adverse events will be registered.

Randomization, blinding and treatment allocation

This is an open-label proof of concept study. There will be no randomization or blinding. All subjects will receive study treatment.

Study Procedures

Prior to performing any study related procedures, the investigator will discuss with each subject the nature of the study, its requirements and its restrictions. A written informed consent form will be obtained from each participant prior to any procedure.

Each subject with a signed informed consent form will be screened at the first visit, to ensure all the inclusion criteria are met and none of the exclusion criteria.

Study procedures are described in detail below and an overview of the study procedures during each visit.

Medical history

- A complete medical history, including history of diabetes, will be taken at screening. The subject's medical history will be updated at the Baseline visit. This updated medical history will serve as the baseline for clinical assessment.
- Demographic information, including subject self-reported gender, race, age, ethnicity, and child-bearing potential will be recorded.
- Nicotine and alcohol history will be obtained

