- NLD history: Date of onset of NLD, all previous and current medical and procedural treatments for NLD, and reasons for discontinuation or outcomes of previous treatments will be obtained.

Vital signs

Vital sign determinations of systolic and diastolic blood pressure, pulse rate, and body temperature will be obtained at visits as specified in the Overview of Study Procedures. Blood pressure and pulse rate should be measured after the subject has been sitting for at least 3 minutes.

Complete Physical exam, including height and weight.

Height will be measured at screening only. Body weight will be measured at all scheduled visits as specified in Overview of Study Procedures. The subject will wear lightweight clothing and no shoes

during weighing. A complete physical examination, including cutaneous examination to evaluate for skin malignancies, will be performed at the designated study visits as specified in Overview of Study Procedures. The physical examination performed on Study Day 0 will serve as the baseline physical examination for the entire study. If appropriate, a targeted physical exam should be performed at any other visit (e.g., to evaluate a reported adverse event). Any significant physical examination findings after the first dose will be recorded as adverse events, while any findings prior to the first dose will be recorded as medical history. All findings, whether related to an AE or part of each subject's medical history, will be captured on the appropriate AE report form. At any time, a symptom-directed physical examination can be performed as deemed necessary by the Investigator.

Efficacy assessment:

IGA of Disease Severity will be performed by the investigator. Patient-reported outcomes, including DLQI and Pain score, will be administered to subjects as subject questionnaires prior to any assessment of disease severity or laboratory testing. See Overview of Study Procedures for schedule and Study Parameters for further details on efficacy assessments.

Laboratory Testing

Blood samples will be collected at scheduled visits as listed in Overview of Study Procedures. A certified laboratory at Beth Israel Deaconess Medical Center (BIDMC) through the Clinical Research Center will be utilized to process and provide results for the clinical laboratory tests.

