Laboratory reference ranges will be obtained prior to the initiation of the study. The Baseline laboratory test results for clinical assessment for a particular test will be defined as the last measurement prior to the initial dose of study drug.

Whether action needs to be taken to address notable laboratory values will be decided by the investigator, taking into account the overall status of the subject.

The following laboratory tests will be performed according to the study procedures schedule listed in Overview of Study Procedures:

- Complete Blood Count (CBC): automated WBC, RBC, hemoglobin, hematocrit, platelet count

and RBC indices

- Complete Metabolic Panel (CMP): Sodium, Potassium, Chloride, Bicarbonate, BUN, Creatinine, Glucose, Alk Phos, ALT, AST, Total Bilirubin, GGT, Albumin, Albumin/Globulin Ratio (calculated), BUN/Creatinine Ratio (calculated), Calcium, Globulin (calculated), Total Protein
- HIV: HIV1&2 Antibody/Antigen Combo Assay
- Hepatitis B: Hep B Core Ab (Hep B Cab), Hep B Surface Antigen (Hep B Sag), and Hep B surface antibody (Hep B Sab)
- Hepatitis C: Hepatitis C antibody
- Tuberculosis: Quantiferon-TB Gold

Subjects who test positive for TB (quantiferon gold), Hepatitis C antibody, or Hepatitis B Sag or Hepatitis B Core antibody will be excluded from the study. Patients with a positive quantiferon gold will be referred to ID. If a patient has an indeterminate quantiferon gold that test will be repeated. If there are two indeterminate quantiferon gold results, then the patient will be referred to ID. If ID thinks the patient (with an indeterminate quant gold) needs to be treated for latent TB, then the patient will be treated for latent TB (see below). If ID does not think the patient (with an indeterminate quant gold) needs treatment for latent TB then the patient will be eligible to enroll in the clinical trial

After one month of treatment for latent TB, a subject would be considered eligible for participation in the trial.

Skin Biopsy

A 4 mm punch biopsy will be obtained from lesional skin at the baseline and week 26 visit. Skin biopsy location will be determined by the investigator and standard procedures for skin biopsy will be employed. Subjects may have lesions closed with suture or gelfoam, depending on nature of lesion and biopsy.

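### The rule for examination-based adverse events sorts findings by date rather than by change from Day 0, and it sends medical-history findings to the AE form

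*Combined protocol and SAP*

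**What the plan says.** The rule is in the combined protocol and SAP, section B3.A, Study Procedures, in the paragraph on the complete physical examination. Four statements there bear on the point:

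- Baseline: "The physical examination performed on Study Day 0 will serve as the baseline physical examination for the entire study".
- After the first dose: "Any significant physical examination findings after the first dose will be recorded as adverse events".
- Before the first dose, in the second half of that same sentence: "any findings prior to the first dose will be recorded as medical history".
- Where it is written down: "All findings, whether related to an AE or part of each subject's medical history, will be captured on the appropriate AE report form".

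Other parts of B3.A also define baselines. Of the medical history updated at the Baseline visit, the protocol says "This updated medical history will serve as the baseline for clinical assessment". The baseline value of a laboratory test "will be defined as the last measurement prior to the initial dose of study drug".

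Under Safety Parameters, adverse events are to be registered at every visit. The Statistical Considerations section describes the trial as a feasibility and tolerability pilot. It gives no analysis of adverse events and no treatment-emergent definition.

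**The concern.** The post-dose rule has two conditions: the finding is significant, and it is seen after the first dose. Neither asks whether anything has changed. This population has skin disease at entry by design, since inclusion criterion 3 begins "Active NLD lesions, defined as", and the complete examination includes the skin. Findings that are present on Day 0 and persist are therefore to be expected.

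Tolerability is one of the reasons given for running the study, and there is no control arm. Comparison with the subject's own baseline is then the main internal safeguard when an examination finding is read as a possible effect of treatment. A recording rule that leaves this comparison out, together with a form instruction that mixes medical history with adverse events, can put pre-existing findings into the AE count.

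**Working it through.** The plan states no AE rate or AE calculation, so there is no figure to reproduce. The check is to apply the text to each possible course of a significant finding, then see what one misclassification is worth.

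**Classification.** The schedule of procedures places complete examinations at Screening, Baseline, Week 8 and Week 24. Targeted examinations are allowed at other visits. Take Week 8 as the example.

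| Day 0 | Week 8 | Rule as written | Rule based on change from Day 0 |
|---|---|---|---|
| Absent | Present | AE | AE |
| Present | Worse | Medical history at Day 0; AE at Week 8 | Medical history at Day 0; AE at Week 8 |
| Present | Unchanged | Medical history at Day 0; AE at Week 8 if read literally | Medical history only |
| Present | Resolved | Medical history only | Medical history only |

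The two rules differ only in the third row. There the finding meets the pre-dose clause on Day 0 and the post-dose clause at Week 8, and nothing in the paragraph says which prevails. One staff member may silently read the post-dose clause as limited to new findings, while another may follow it literally.

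**Form.** One sentence places pre-dose findings in medical history. The next captures every finding, including those that are medical history, on the AE report form. The second sentence does not say how the two kinds of entry are to be told apart on that form.

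**Size.** Inputs: N = 18 planned subjects (B3.A, Population), and k = number of subjects counted as having an AE only because of an unchanged pre-existing finding. The documents do not give k.

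- Shift in incidence = k / N.
- For k = 1: 1 / 18 = 0.056, or 5.6 percentage points.

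The B3.A text on a call after study completion mentions three subjects who completed and one who terminated early. If only those four were reported, which is an assumption, the shift per subject would be 1 / (3 + 1) = 25 percentage points.

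The shift applies when the subject has no genuine event in the category being counted. A subject who already has one adds nothing to the incidence, although the number of events still rises.

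**The case against.** The strongest reply is that the sentence should be read whole. Its second half already assigns a Day 0 finding to medical history, and nowhere does the protocol say that an unchanged finding is reclassified later. A sensible investigator would read the first half as meaning new findings. That is a fair account of the likely intent, and it limits the point to what the text permits rather than what it commands. It does not remove the gap, because the limiting words are absent and the next sentence adds a conflict of its own.

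Several stronger conclusions are tempting, and the documents do not support them:

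- A reader might infer that the AE data cannot separate drug effects from baseline disease, or new ulceration from ulceration at entry. The Day 0 examination and the updated history are named baselines. The IGA and photographs are scheduled from Baseline through Week 24, and the IGA has separate levels for no change and for worsening. Separation remains possible; the rule simply does not call for it.
- A reader might infer that, since every subject enters with active lesions, all 18 would show an AE. That is a ceiling under the most literal reading. It needs every lesion to be judged significant and to persist, and the documents give no such rate.
- A reader might expect sites to differ in applying the rule. All study visits take place at one centre, so any variation would be between staff.
- A reader might count the biopsy scar as contamination by baseline disease. It arises from a study procedure, and a rule based on change from Day 0 would generally still treat it as new.

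It is also fair to say that the rule governs examination findings only, that no AE incidence endpoint is defined, and that better wording would not remove the limit on attribution set by a single arm with no stated assessment of relatedness.

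**Conclusion.** The point stands as a wording fault with a practical consequence. The rule classifies examination findings by timing alone, despite a named Day 0 baseline, and the instruction on forms conflicts with the sentence before it. Followed literally, it can count persisting pre-existing findings as adverse events and inflate examination-based AE counts.

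How far it would do so cannot be estimated from the documents. The 5.6 points is the effect of one misclassified subject at the planned size, not a forecast. It assumes that staff follow the literal text and that the subject has no true event of the kind counted.

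Adverse events registered by other routes and the primary endpoint are not affected. The fault does not threaten the study, but it bears on tolerability and should be corrected.

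**What to change.** Replace the two sentences with wording to this effect: significant examination findings after the first dose that are new, or worse than at the Day 0 examination, are recorded as adverse events; findings present before the first dose are recorded on the medical-history form and do not go on the AE form unless they worsen.

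For subjects already treated, apply the same definition to the recorded entries before reporting, using the Day 0 examination and the baseline history as the reference.

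The cost is a few sentences, a form instruction and a small amount of re-sorting of existing entries. No new assessment is needed, because the Day 0 examination is already in the schedule.
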